The overarching goal of the proposed study will be to replicate and extend these very encouraging initial findings by 1) increasing the dose of RET (3 vs. 2 sessions) so as to bolster treatment effects, 2) employing fMRI methods to identify patterns of brain activity (BOLD signal changes in regions of interest, ROIs, and functional connectivity) uniquely associated with R-E training and potentially predictive of treatment outcome, and 3) extending follow-up period to more completely assess the long-term effects of RET. Two groups of treatment-seeking smokers will remain abstinent overnight prior to undergoing a baseline cue reactivity assessment and fMRI session (only a portion of each group will undergo fMRI pre- and post-treatment. On their target-quit day, a three-day intervention phase will begin. On each day, Group R-E will receive RET whereas Group NR-E will first be administered retrieval cues that do not contain smoking content (NR) and then receive extinction training (E). The next day, all groups will undergo a cue reactivity assessment and fMRI session identical to baseline. This will end a four-day period of compensated abstinence designed to limit the possibility of reinforcing smoking memories via nicotine administration. Both groups will monitor their smoking behavior and undergo identical laboratory test sessions over a 6-month follow-up period. The aims/hypotheses are:

**Aim 1:** Assess the acute and long-term effects of R-E training on indices of smoking behavior/relapse.

**H1)** Relative to control, Group R-E will show decreased smoking (CPD) during follow-up.

**Secondary H1)** Relative to control, more participants in Group R-E will achieve a 60% smoking reduction (from baseline) during follow-up.

**Aim 2:** Assess RET effects (vs. baseline/control) on fronto-limbic-striatal circuitry function & behavior.

**H2.a)** Cue reactivity: Group R-E will evidence attenuated CR BOLD in medial prefrontal cortex (mPFC: dorsal anterior cingulate-dACC; ventromedial: vmPFC), limbic regions (amygdala, hippocampus) and ventral striatum. Greater reduction in BOLD response in regions of interest will predict decreased smoking.

**H2.b):** Group R-E will evince strengthened resting-state functional connectivity (rsFC) between mPFC regions and ventral striatum (frontostriatal circuits), reduced rsFC between mPFC and amygdala (frontolimbic); and the relative magnitude of change in rsFC will be inversely related to craving and smoking (e.g., CPD).

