**Fig. 2b** depicts the mean self-report CPD smoked (left axis, solid symbols) and expired CO levels obtained (right axis, empty symbols) at Baseline, 2-week and 1-month follow-up. Group R-E evidenced lower mean CPD than Group NR-E at both 2-week and 1-month follow-up (adjusted for baseline CPD, sex, years of regular smoking, and negative affect;  $p = 0.024$ ,  $d = 0.50$ ). Further, expired CO level was lower in Group R-E vs. NR-E at 1-month follow-up (adjusted for negative affect and race;  $p = 0.033$ ,  $d = 0.47$ ). Thus, the self-report smoking and CO findings indicate that RET confers a smoking reduction advantage over extinction training alone. Specifically, Group R-E evidenced a 25% greater reduction in smoking than group NR-E. **Fig. 3** depicts group level CPD smoked each day post-treatment. The figure clearly shows that RET had immediate effects on smoking and that the group difference persists unabated over the follow-up. In fact, this figure, together with the CO outcomes, suggests the possibility that the effect magnitude may be increasing during the latter 2-week period of follow-up. Lastly, there was trend level evidence that a greater percentage of participants in Group R-E (51.5%) vs. NR-E (25.6%) achieved a 60% reduction in smoking (from baseline) during follow-up (risk ratio (RR)=1.62 (0.98-2.67),  $p=.06$ ; At 2-week and 1-month follow-up time points, the  $p$ 's=.18 and .04, respectively)

We believe these results are very impressive, especially when one considers the modest difference in treatment between the two groups (i.e., a 5-minute smoking- vs. neutral-content

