E vs. control groups. However, the sample size in a repeated measures design is reduced when assuming a 1st order autoregressive error covariance structure with rho=0.9 (previous studies range 0.80-0.95). The number of participants per group required to achieve this power is therefore estimated to be n=62; however, this number needs to be adjusted for dropout between randomization and end of study. While the R21 dropout rate was 19.4%, this study will include a longer compensated abstinence period and longer follow-up period, which may increase dropout to 25%. Therefore, **83 participants** will be randomized per group after adjusting for dropout. Secondary Hypothesis 1b: Studies have shown that smokers with larger reductions in CPD may have increased odds of cessation compared to those with smaller reductions. Preliminary analysis from the R21 showed that 52% of participants in Group R-E had achieved a  $\geq 60\%$  reduction in CPD during the 2 weeks leading up to the 1 month follow-up visit relative to the 2 weeks prior to study treatment while only 26% of Group N-RE achieved the same milestone. The randomized sample size of 83 participants per group (62 completers) will provide greater than 80% power ( $\alpha < .05$ ) to detect a similar difference between group R-E relative to each control group. Hypothesis 3: In the R21, cue-elicited craving was measured during post-treatment test sessions at 24-hrs, 2-wks and 1-mo. In the 1-mo test session, differences between R-E and NR-E groups emerged, showing a decrease in cue-elicited craving in Group R-E as compared to Group NR-E ( $d=0.44$ ). In the proposed study, data will be collected at each of the 7 test sessions (over 6-months) and we assume an attenuated effect size (for the same reason noted above for CPD) relative to the R21 findings ( $d=0.40$ ). Given a moderate Rho ( $=0.5$ ), the sample will provide greater than 80% power to detect an effect size of  $d=0.4$  between Group R-E and controls. Thus, the sample size of **83 participants per treatment group (n=166 total)** will provide sufficient power ( $\geq 80\%$ ; and  $\alpha < .05$ ) to detect clinically meaningful smoking efficacy and craving differences for group R-E compared to controls, after accounting for up to 25% dropout.

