## 12.0 Data Management

Baseline demographic and clinical measures will be compared across groups using standard statistical methods (e.g., Chi square test of independence for categorical variables; Univariate ANOVA for continuous variables). Characteristics that (i) display imbalance at baseline, (ii) are associated with a dependent measure, or (iii) are known to be predictive of study outcomes (e.g., craving, smoking) will be assessed for inclusion as covariates in the final models. **Primary Aims Analysis:** The primary hypothesis of Aim 1 is that Group R-E will evidence decreased smoking behavior during follow relative to both control groups. Smoking behavior will be measured via smoking diary/TLFB recovered at each visit or by phone, from which, the mean CPD will be calculated between each visit for the period until the last attended visit. Additionally, the smoking diary/TLFB data will be used to compute an indicator of those that achieved a  $\geq$ 60% reduction in CPD relative to baseline smoking at each visit. Generalized linear mixed effects models will be used to analyze the longitudinal smoking behavior data during follow up (using appropriate

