distributions). Overall statistical significance for the effects of treatment group, time, and their interaction will be assessed using a likelihood ratio test that compares the final model to a model consisting of an intercept term alone. The pre-specified hypothesis will be tested using model-based estimates to construct group comparisons across all the planned time points. Normality of residuals will be tested for models where appropriate and when found in error, appropriate transformations or non-parametric methods will be employed. Although mixed effects models have been proven highly efficient in cases where follow up data is missing at random, to accommodate other types of missing data, we will perform analyses using multiple imputation methods (Bayesian approach using both MCMC and FCS). The primary hypothesis associated with Aim 3 is that Group R-E will evidence decreased cue-elicited craving during follow-up testing. General linear mixed effects models will be constructed to assess group differences in craving over time. **Secondary Analysis:** Smoking relapse (i.e., days to 3 consecutive days of smoking ≥5 cigarettes) will be tested using a Cox Proportional Hazards regression model. Log-Log plots of the survival function and inclusion of a time variable treatment term will assess the proportionality assumptions and if models fail this assumption, a stratified Cox Regression model will be used. Also, we will measure end of study 7-day point prevalence abstinence as well as continuous abstinence using smoking diary/TLFB data. The effect of R-E training on abstinence outcomes will be tested using logistic regression models. **Biological Variables:** Exploratory analysis of sex effects on study outcomes will be assessed through main effects and the interaction between sex and study treatment assignment. Where significant interactions are found, sex stratified analyses will be conducted to assess the role of sex in the effect of RET on study outcomes. **Other secondary analyses** will assess i) differences between the control groups on main outcomes, ii) craving and cue reactivity differences during the three intervention sessions, and iii) the effects of treatment on ambient or background craving and cue reactivity (i.e., non-cue-elicited outcomes obtained early in test sessions). All analysis will be conducted using SAS/STAT v. 9.4 and Stata v. 14.

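### The pilot rates behind Secondary H1 disagree with the risk ratio printed beside them and carry two time windows, so the >80% power covers only a single-visit contrast; the imputation plan also claims too much

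*Combined protocol and SAP*

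**What the plan says.** **Pilot result (section 2.0, part B, Results).** The R21 is summarised as showing that "a greater percentage of participants in Group R-E (51.5%) vs. NR-E (25.6%) achieved a 60% reduction in smoking (from baseline) during follow-up". The effect printed beside it is "risk ratio (RR)=1.62 (0.98-2.67", with p = .06. The same sentence then gives separate p values, "At 2-week and 1-month follow-up time points", of .18 and .04.

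**Power statement (section 10.0 iii).** The same rates, rounded to 52% and 26%, are said to have been reached "during the 2 weeks leading up to the 1 month follow-up visit". On that basis the plan states: "The randomized sample size of 83 participants per group (62 completers) will provide greater than 80% power" at alpha .05, for a difference similar to the pilot's.

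**Hypothesis and analysis.** Section 1.0 words Secondary H1 as: "more participants in Group R-E will achieve a 60% smoking reduction (from baseline) during follow-up". Follow-up lasts 6 months. Section 12.0 derives an indicator of at least a "60% reduction in CPD relative to baseline smoking at each visit", analyses it with generalized linear mixed models, and adds: "The pre-specified hypothesis will be tested using model-based estimates to construct group comparisons across all the planned time points".

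**Missing data (section 12.0).** Mixed models are presented as efficient when follow-up data are missing at random. Multiple imputation by MCMC and FCS is then offered to deal with other kinds of missingness.

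**The concern.** One pair of rates appears under two windows, and beside a risk ratio that it does not produce. The power for Secondary H1 rests on that pair. If the rates belong to the 1-month visit, the power statement describes one visit, and it is the more favourable of the two pilot visits (p = .04, against .18 at 2 weeks and .06 overall). The hypothesis is worded for the whole follow-up. A null result on Secondary H1 could then be read as coming from a test with more than 80% power, when power for that contrast was never stated.

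The imputation wording matters for the same endpoint. The plan allows for 25% dropout, and people who resume smoking may be the ones who stop attending. A reader would believe that this possibility is covered by a planned analysis when, as described, it is not.

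**Working it through.** **1. The plan's own figure.** Inputs from section 10.0 iii: p1 = .52, p2 = .26, n = 62 per group, alpha .05 (two-sided assumed; the plan does not say). Pooled-variance normal approximation, mean rate .39:

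- SE under the null = √(2 × .39 × .61 / 62) = .0876
- SE under the alternative = √((.52 × .48 + .26 × .74) / 62) = .0844
- Power = Φ((.26 − 1.96 × .0876) / .0844) = 85.2%

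Fisher's exact test gives 81.3%. The stated figure reproduces.

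**2. Rates against risk ratio (section 2.0 B).**

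- Ratio of the printed rates: 51.5/25.6 = 2.01 (52/26 = 2.00), not 1.62.
- Printed interval: log-SE = ln(2.67/0.98)/3.92 = .2557; z = ln(1.62)/.2557 = 1.887; p = .059. This agrees with the printed .06, so risk ratio, interval and p value fit one another.
- Printed rates as crude proportions with the randomised 44 and 43: SE = √(.485/(.515 × 44) + .744/(.256 × 43)) = .298; z = ln(2.01)/.298 = 2.34; p = .019. Among denominators up to the randomised numbers, 51.5% is only 17/33, and 25.6% is 11/43 or 10/39. With those, p is .024 to .030.

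As crude rates, then, they give neither the printed risk ratio nor the printed p value.

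**3. Power if the effect is 1.62.** The documents give no rates to go with 1.62, so the pilot's standard error is scaled. Assumptions: same estimator; pilot base of 72 to 88 people (88 recruited; 44 + 43 = 87 randomised; 72 = 87 less the 17.2% in section 10.0 x who did not complete); analysed N of 124 (2 × 62) or 166.

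- SE = .2557 × √(base/N); power = Φ(ln(1.62)/SE − 1.96)
- Example, base 72, N = 124: SE = .195, power = 69.7%. Base 88: SE = .215, power = 61.0%.

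If 1.62 pools the pilot's two visits and this trial averages six, the variance is multiplied by a ratio of AR(1) factors. At rho = 0.9 this is .824/.950 = .867; at 0.8, .680/.900 = .756; at 0.5, .391/.750 = .521. The plan uses 0.9 for CPD and 0.5 for craving, and gives no value for the 60% indicator.

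| Setting, risk ratio 1.62 | 124 analysed | 166 analysed |
|---|---|---|
| No credit for extra visits | 61–70% | 74–82% |
| Six visits, rho 0.9 | 67–76% | 79.5–87% |
| Six visits, rho 0.8 | 73–81% | 85–91% |
| Six visits, rho 0.5 | 87–93% | 95–98% |

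A different approach, one binary comparison with 62 per group, gives 46% if control is 25.6% (41.5% vs 25.6%) and 61% if R-E is 51.5% (51.5% vs 31.8%). The spread shows how far the answer depends on inputs that the documents do not supply.

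**4. Imputation.** MCMC and FCS are ways of drawing imputed values from a model fitted to the observed data. With no shift parameter or pattern-mixture component, and none is described, they assume missing at random just as the mixed model does.

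**The case against.** The strongest reply is that the quoted power sentence is correct, that section 10.0 iii itself discloses the 1-month window, and that comparisons across the planned time points may mean one comparison per visit. On that reading a single-visit 52% vs 26% is a legitimate planning contrast. All of this stands, so the power sentence is not an arithmetic error. What remains is that section 1.0 words the hypothesis for follow-up as a whole, and section 12.0 does not say which comparison decides it.

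The risk ratio of 1.62 may also be a model-based estimate over both pilot visits, with the rates belonging to 1 month. That would explain the mismatch without any miscalculation. It is plausible, but section 2.0 B does not say so, although it labels the neighbouring CPD and CO results as adjusted. It also places these rates under follow-up generally. This supports asking for clarification, not asserting a mistake in the pilot analysis.

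A reader might infer that the trial is underpowered for Secondary H1. The documents do not support that. At a risk ratio of 1.62, power passes 80% in several settings above and falls short in others.

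**Conclusion.** The inconsistency is real but minor. The printed rates imply a risk ratio of 2.01 against the 1.62 beside them, and sections 2.0 B and 10.0 iii attach them to different windows. The >80% holds for 52% vs 26% at one visit (85% with 62 per group, two-sided). Power for a follow-up-wide contrast is unstated and indeterminate: 61–70% with 124 analysed and no credit for extra visits; 67–76% at rho 0.9 to 87–93% at rho 0.5 with six visits; higher with all 166. These ranges rest on the assumed pilot base, estimator and correlation. Secondary H1 does not set the sample size, so the correction is to the text.

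Separately, the statement that the described imputation deals with data not missing at random is incorrect, and the plan contains no analysis that does so.

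**What to change.** Keep 83 per group.

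- **(a)** Reconcile sections 2.0 B and 10.0 iii so that rates, risk ratio and window agree. Say whether 1.62 is model-based, and give the pilot numerators and denominators by arm and visit.
- **(b)** Limit the >80% statement to a single-visit contrast of 52% vs 26%. State which comparison tests Secondary H1. If it is averaged over visits, restate its power with its own rates and an assumed visit correlation, whichever way the figure moves.
- **(c)** Correct the imputation statement in section 12.0. Keep the mixed model and multiple imputation, and pre-state one sensitivity analysis that departs from missing at random: for example, scoring missing 60%-reduction indicators as not reduced, or a delta-adjusted imputation.

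**Cost:** some text, a few counts from data that the investigators hold, and one extra analysis. There is no added enrolment. The sensitivity analysis is conservative. With 25% missing in each arm, scoring missing as not reduced turns 52% vs 26% into 39% vs 19.5% (each × .75), for which power with 83 per group is about 79%.

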fMRI sample size estimation. Though we have not assessed the effects of RET on fMRI BOLD response, the four human fear conditioning studies of RET described above reported significant BOLD and connectivity changes with n's ranging from 19 to 23. Additionally, some of our previous work provides strong support that we will observe significant effects with group n's in this range. In two prior fMRI CR studies of smoking/smoking abstinence (n's=17-19), effects sizes for CR-BOLD response ranged between  $d=.65$  to 1.5. In two prior rsFC studies in cigarette smokers (n's 16-18), we found smoking abstinence, compared to satiety, strengthened rsFC in an amygdala-striatal circuit ( $rZ$ 's between .56 and .91); whereas in Froeliger et al 2015 the strength of rsFC in the frontostriatal pathway was associated with less craving ( $R^2=.48$ ) and smoking (CO confirmed:  $R^2=.50$ ). In the proposed study, we will examine the effects of RET on drug CR-BOLD response (Hypothesis 2a) and rsFC (Hypothesis 2b). If we assume, based on our prior work and that of others, that these effects are of medium to large size (e.g.  $D \approx .8$ ), then with a full fMRI sample of N=68 (34 per group) and  $\alpha =.05$  (1-tailed), a final sample of  $\approx 23$  participants in each group (accounting for fMRI ineligibility and 30% attrition) will result in power  $>.80$  for detecting effects on CR-BOLD response and rsFC.

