Validity and data integrity will be checked on an ongoing basis through the use of data audits. Study statisticians ([name]/[name]) will supervise quarterly data quality assessments (i.e., examination of the outcomes database(s) for missing data, unexpected distributions or responses, and outliers) performed by the study research staff. Accuracy and completeness of the data collected will be ensured by weekly review. A 10% random sample of the primary source document will be crosschecked with the database on a quarterly basis. If inaccuracies exceed 2%, then a second 10% will be randomly chosen for audit. Should data discrepancies be discovered, they will be resolved using original source documents. The REDCap system does not accept outliers, illogical response patterns, etc. The PI will have weekly meetings with the research staff to discuss qualitative comments received during data collection and any problems in data collection or entry. The statistician will periodically examine the database to look for irregularities. Initial data analyses will examine distributions of variable scores and comparability of baseline characteristics across conditions in case analyses need to be adjusted for these.

**fMRI Analysis Plan.** The hypothesis for 2a (CR) is that Group R-E will evidence attenuated CR in medial prefrontal cortex (mPFC: dorsal anterior cingulate-dACC; ventromedial: vmPFC), limbic regions (amygdala, hippocampus) and ventral striatum. Greater reduction in BOLD response in regions of interest will predict decreased smoking. fMRI data will be preprocessed using recommended procedures in SPM8 and as done previously. At the 1st-level, data will be analyzed using the GLM; events of interest (Smoking, Neutral) will be modeled as a boxcar canonically convolved hemodynamic response function, and HR and motion parameters entered as nuisance covariates. At the 2nd-level, 2 (Time: Pre, Post) x 2 (Group: R-E, NR-E) ANOVA will be used within an *a priori* ROI mask (amygdala, hippocampus, mPFC, ventral striatum;  $p < .05$ , pFWE). **Hypothesis for 2b (rsFC)** is that group R-E will evidence strengthened rsFC in frontostriatal circuitry; weakened rsFC in frontolimbic circuitry and the magnitude of rsFC will be inversely related to craving and smoking (e.g., CPD). **fMRI data analysis plan.** Similar to our previous work along with in scanner heart-rate and respiration entered as covariates, rsFC will

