be assessed using the conn13 SPM8 toolbox. Connectivity matrix for each seed (see ROI mask in 2a) will be entered into separate: 2 (Time: Pre, Post) x 2 (Group) ANOVA. Exploratory voxel-wise analyses are planned for 2a and 2b with specific focus on subdivisions of the insular cortex (cf., Addicott et. al., 2015).

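### The fMRI power above .80 is for one uncorrected one-tailed test; the analysis plan names Time x Group ANOVAs, does not carry over the one-tailed contrast, and applies FWE correction to H2a

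*Combined protocol and SAP*

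**What the plan says.** The fMRI sample size paragraph (section 10.0, iii) starts from 68 scanned participants, 34 per group. It assumes "that these effects are of medium to large size (e.g"., D of about .8), sets alpha at .05 ("1-tailed), a final sample of" about 23 per group), and concludes that these "participants in each group (accounting for fMRI ineligibility and 30% attrition) will result in power" above .80 for effects on both cue-reactivity BOLD (H2a) and resting-state connectivity (H2b). It mentions no multiplicity correction. It does not say whether D is a group difference in pre-post change or in the post-treatment value.

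The fMRI Analysis Plan (section 12.0) sets out the tests. For H2a, a "2 (Time: Pre, Post) x 2 (Group: R-E, NR-E) ANOVA will be used within an" a priori "ROI mask (amygdala, hippocampus, mPFC, ventral striatum"), with the threshold at p < .05, FWE-corrected. For H2b, "Connectivity matrix for each seed (see ROI mask in 2a) will be entered into separate" Time x Group ANOVAs, with no correction across seeds stated.

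Both hypotheses are directional. H2a predicts attenuated reactivity in Group R-E, and H2b predicts "strengthened rsFC in frontostriatal circuitry; weakened rsFC in frontolimbic circuitry and the magnitude of rsFC will be inversely related" to craving and smoking. The analysis plan does not turn these directions into a one-tailed contrast or threshold.

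**The concern.** A power statement describes one test at one threshold. The one in section 10.0 differs from the tests in section 12.0 in two ways.

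- **FWE correction.** H2a is judged at a corrected threshold across a mask of four regions, while the power was computed at an uncorrected .05. A stricter threshold lowers power for any given region.
- **Sidedness.** The power is one-tailed. The analysis plan names ANOVAs, and the usual F test of a Time x Group interaction is two-sided. Nothing in section 12.0 says that a directional contrast replaces it.

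A reader who takes .80 as the power for a named region or circuit would put more weight on a null Aim 2 result than the design supports. Leaving the contrast open also allows the choice between a one-tailed contrast and an F test to be made after the data are seen.

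**Working it through.** **Inputs.** From the fMRI sample size paragraph: d = .8, n = 23 per group (34 x 0.70 = 23.8 before any allowance for MRI ineligibility), alpha = .05 one-tailed. From the fMRI Analysis Plan: Time x Group ANOVA, and FWE p < .05 over four regions for H2a. Assumption: d is the group difference in pre-post change divided by the SD of change.

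**Equivalence.** With two groups and two times, the interaction F has 1 numerator df and equals the square of the two-sample t on change scores. One noncentrality therefore serves both tests:

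- df = 2 x 23 − 2 = 44
- ncp = d x sqrt(n/2) = .8 x sqrt(11.5) = 2.71
- lambda = n x d²/2 = 23 x .64/2 = 7.36

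**Step 1: the plan's figure.** Noncentral t, df 44, ncp 2.71, one-tailed .05: power .848. The claim of more than .80 reproduces.

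**Step 2: the interaction F test.** Noncentral F(1, 44), lambda 7.36, alpha .05: power .756. The two-sided t gives the same. Power by n per group is .791 at 25, .807 at 26 and .822 at 27, so .80 is first reached at 26. At n = 23 it would need d of about .845.

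**Step 3: correction for H2a.** Power under voxel-wise FWE depends on quantities that the documents do not give. As an illustration only, Bonferroni over the four regions uses alpha = .05/4 = .0125.

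| Test at n = 23, d = .8 | Uncorrected | Given region, Bonferroni over 4 (illustration) |
|---|---|---|
| One-tailed contrast | .848 | .653 |
| Two-sided F test | .756 | .547 |

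**Step 4: the scale of d.** If .8 is instead on the post-treatment score, with equal variances and pre-post correlation r, then d for change = .8/sqrt(2(1 − r)).

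| r (assumed) | d for change | One-tailed | Two-sided F |
|---|---|---|---|
| 0 | .566 | .596 | .467 |
| .3 | .676 | .730 | .611 |
| .5 | .800 | .848 | .756 |
| .7 | 1.033 | .964 | .929 |

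The documents give no pre-post correlation, so this range cannot be narrowed. All figures here are uncorrected.

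**The case against.** **Sidedness is silence, not contradiction.** Section 10.0 is the only place that states sidedness for H2a and H2b, and it says one-tailed. Both hypotheses are directional, section 12.0 nowhere says two-sided, and a 1-df interaction can be tested as a directional contrast. This stands. A reader might infer that the protocol plans a two-sided test and contradicts its own power calculation; the documents do not support that. The .756 applies only if the ANOVA is read as the usual F test. What remains is that the contrast has to be written into the analysis plan. The one-tailed setting is not a protocol-wide convention that could be assumed: the 78 per group for cigarettes per day at d = .45 reproduces as a two-sided calculation (2 x (1.96 + .84)²/.45² = about 77.5).

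**The inputs are approximate and the attrition allowance is cautious.** This also stands. At n = 24 the F test has power .774, and at d = .85 with n = 23 it has .805. At the R21 dropout of 19.4%, 34 x .806 = 27.4, so 27 per group remain and power is .82. The Intervention section reports 10% discontinued during R21 treatment. That loss would leave about 30 per group and power .86, before any MRI ineligibility or missed scans. So a reader should not infer that Aim 2 is underpowered. The two-sided shortfall is tied to the planned 23 per group.

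**The FWE loss is not quantified.** Correct. The .65 and .55 are a Bonferroni illustration and should not be read as the power of H2a. General Neuroimaging Methods (section 10.0, vi) presents the ROI mask as a way to limit the number of voxels tested. That reduces the cost of correction but does not remove it. None of this makes an uncorrected figure describe a corrected test.

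**Aim 2 is mechanistic and the trial is sized on Aim 1.** True, and it limits the importance. The protocol nevertheless makes an explicit power claim for both imaging hypotheses.

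**Conclusion.** The point holds as a mismatch between the test that was powered and the tests that are planned. The arithmetic in section 10.0 is right for its stated inputs. What it describes is one one-tailed test at .05 with no correction, and it cannot be cited as the power for a given H2a region.

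If d = .8 is the group difference in change in SD-of-change units and 23 per group are analysed, uncorrected power is .85 for a one-tailed contrast and .76 for the interaction F test. A true effect of that size would be missed about 15% or 24% of the time. For a given H2a region, power after FWE is lower by an amount the documents do not allow one to compute. For H2b, section 12.0 states no correction, so only sidedness and the scale of d are at issue.

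The mismatch over FWE and the missing contrast do not depend on how d is defined; the numerical values do. This should be corrected, but it does not call the sample size of the trial into question.

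**What to change.** Choose one of two wordings:

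1. **Specify the contrast.** In the fMRI Analysis Plan (section 12.0), state a one-tailed Time x Group contrast in each predicted direction for H2a and H2b. The stated power then stays at about .85, uncorrected. The price is that an effect in the opposite direction cannot be confirmatory.
2. **Keep the F test.** Restate the fMRI sample size paragraph (section 10.0, iii) as power of about .76 at 23 per group for one two-sided Time x Group test. The price is a stated power below .80.

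With either choice, define d in section 10.0 as the group difference in pre-post change in SD-of-change units. Add there that the figure is for one test before the planned FWE correction, and so is not the power for a given H2a region.

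The cost is protocol wording only, with no added participants or scans. It should be settled before the imaging data are analysed.
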